## Outcomes

### Baseline Data

At the beginning of the trial, an initial evaluation was performed to assess the severity of ASD in participants using the CARS score. Table 1 displays the mean, median, and range of the participant scores. Most participants had moderate to severe ASD, with a CARS score higher than 35. There were no significant differences in age, gender, ethnicity, language status, treatment status, or CARS scores between the Active and Sham groups.

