## 2.4 Results of the Previous Pilot Study using the same device

[figure not shown]
Our recently concluded pilot study collaborates these predictions. We enrolled 30 participants who were 2-6 year old (16 in active and 14 in sham-control condition). Participants in the active condition have improved significantly (as measured by Childhood Autism Rating Scale). Participants in the sham condition showed no such improvement (see Chart 1). Furthermore, EEG data showed reduction of Delta waves over the course of the study for the participants of Active condition only (see Chart 2). Frolich et al (2021) reported that high amplitude Delta waves in the wakeful state are associated with neurological disorders and mitochondria disorders. Therefore, this reduction of Delta waves is a signature of the brain healing process (see attached presentation by Naviaux, 2021). Lastly, the change in Delta correlated significantly with the change in CARS showing that the kids whose CARS scores reduced (reflecting their reduction of symptoms) also experienced reduction in their Delta waves (see Chart 3). Lastly, we also found an increase in Theta waves in the children, whose CARS score decreased (inverse correlation between intensity of Theta and CARS scores, see Chart 4). Recent research has shown that there is an insufficient intensity of Theta waves in the children diagnosed of ASD (e.g., Ortiz-Mantilla et al, 2019). This redistribution of brain waves from Delta to Theta in the active condition is signaling of the healing that's happening as a result of treatment with tPBM.

(See attached Charts 1-4 with exact statistics below).

[figure not shown]
**Chart 1:** There was a significant reduction in CARS score in the Active Condition only ( $F=6.47$ ,  $p<.05$ ).

[figure not shown]
**Chart 2:** Delta Waves reduced in the Active Condition: Pearson's R squared  $-.45$ , ( $p<.05$ ,  $n=9$ ) However, this correlation was not significant for the Placebo Condition, Pearson's R squared is  $-.1$ , ( $p>.1$ ,  $n=8$ ).

**Chart 3:** The study revealed a statistically significant correlation between the change in CARSII scores and Change in Delta waves (n=15). Specifically, children (mostly in Active condition), who experienced reduction in CARSII also experienced reduction in Delta waves.

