### 4.0 Inclusion and Exclusion Criteria:

Inclusion Criteria:

1. Male or female participants between 2 years and 7 years of age (inclusive), of all races.
2. Previously diagnosed with moderate or severe ASD by a licensed professional.
3. Participants may be receiving any behavioral intervention therapy (e.g., ABA, Floor Time) during the course of the treatment. The final statistical analysis will control for the participants receiving behavioral therapies in control and experimental conditions. We expect the majority of the participants in both

control and experimental conditions to be receiving behavioral therapies. There is no known interactions or complications of tPBM with behavioral therapy.

4. Parents of participants must understand the nature of the study.
5. Parents of participants must sign an IRB- approved informed consent form before initiation of any study procedures.
6. Parents of participants must have a level of understanding sufficient to communicate with the investigator and study coordinator, and to cooperate with all tests and examinations required by the protocol.
7. Participant child experiencing a major psychiatric disorder will be allowed to participate in the study provided they do not meet any exclusionary criteria.
8. The participant child is willing to participate in this study.
9. Participant previously participated in the JelikaLite pivotal clinical trial that took place in 2021, either in the active or placebo conditions.

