# Data Collection and Statistical Analysis

## Primary Analyses

The last author, a licensed psychologist experienced in the use of CARS in clinical practice, conducted blinded Before and After CARS ratings for all participants. The final CARS evaluations were performed immediately after the final treatment session. CARS scores were analyzed using the independent sample t-test. We compared the differences from the baseline between both groups, calculating both the average difference and 95% CI within each group and between groups.

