### Primary Outcome

Every participant who completed the trial was evaluated with CARS post-treatment. There were no missing CARS posttreatment evaluations. In the Active group, the before treatment CARS scores had a mean score value of 43.5 (n = 16) with a standard deviation (SD) of 5.7, the after-treatment scores had a mean score of 33.7 with an SD of 5.0. In the Sham group, the before treatment CARS scores had a mean score value of 40.6 (n = 14) with SD of 7.2, the after-treatment scores had a mean score of 38.0 with SD of 8.4. Table 3 shows the mean (M) and SD of the CARS scores for the Active and Sham groups before and after treatment. The difference in the change in CARS between the two groups was 7.23 (95% CI 2.357 to 12.107, p=0.01).

In addition to analyzing the changes in CARS scores based on averages, we also conducted respondents-based analyses, quantifying the number of participants in Active and Sham groups, whose change in CARS was greater than 4.5 points (as it has been suggested by Jurek et al 2022 to be the minimal clinically important difference). The result was significant  $\chi^2=8.48$ ,  $p=.004$ . By the end of the trial, 87% of the participants in the Active group (14) had achieved an equal or greater than 4.5-point reduction in CARS scores, only 35% of the participants of Sham group (5) achieved an equal or greater than 4.5-point reduction in CARS scores. The number of subjects that achieved this minimal clinically important difference in the Active group was statistically significantly higher compared to the Sham group. Therefore, the treatment was considered to have clinically meaningful efficacy.

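### The protocol announces control for behavioural therapy, but the SAP shows only unadjusted comparisons, and non-significant baseline tests in 16 v 14 children are not evidence of balance

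*SAP*

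**What the plan says.** **Protocol.** Inclusion criterion 3 (section 4.0) allows behavioural therapy during treatment and adds: "The final statistical analysis will control for the participants receiving behavioral therapies in control and experimental conditions". Section 14.0 says that age, gender and number of therapy hours will be used for matching when children are assigned to control or treatment. Elsewhere the protocol describes a one-arm, open-label study (section 1.0) with a single active condition (section 7.2), analysed by repeated-measures t-tests (section 7.6).

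**SAP.** Primary Analyses states: "CARS scores were analyzed using the independent sample t-test", applied to differences from baseline between two groups. Primary Outcome adds a chi-square on the proportion passing a 4.5-point reduction. No covariate is named in the visible text. On baseline, the SAP says: "There were no significant differences in age, gender, ethnicity, language status, treatment status, or CARS scores between the Active and Sham groups". It does not define treatment status, and the visible text gives no p-values or standardised differences.

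The SAP's group sizes match those the protocol gives for its previous pilot (section 2.4): "16 in active and 14 in sham-control condition".

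**The concern.** The children could receive any behavioural therapy alongside the device, and therapy may itself change CARS. If the two groups differed in therapy or age, part of the 7.23-point difference could belong to that imbalance. The protocol names the remedy, control in the final analysis, but the SAP text shows none.

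The only visible information on balance in therapy is a non-significant test. In a sample this small, such a result fits both good balance and a sizeable observed gap, so it cannot tell the reader whether adjustment would matter. The SAP's conclusion that the benefit is clinically important therefore rests on two comparisons, neither of which accounts for therapy.

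**Working it through.** **Inputs**
- Active, before treatment (SAP, Primary Outcome): "the before treatment CARS scores had a mean score value of 43.5 (n = 16) with a standard deviation (SD) of 5.7".
- Sham, before treatment (same section): "the before treatment CARS scores had a mean score value of 40.6 (n = 14) with SD of 7.2".
- After treatment (same section): 33.7 in Active, 38.0 in Sham.
- Printed result: 7.23, 95% CI 2.357 to 12.107, p = 0.01.
- Assumed, because the documents do not say: baseline tests two-sided at 5%; a covariate imbalance of 0.5 SD; a correlation of 0.3 to 0.5 between covariate and CARS change.

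**1. Reproduce the printed result.** The reductions are 43.5 − 33.7 = 9.8 and 40.6 − 38.0 = 2.6, a difference of 7.2. This agrees with 7.23 apart from rounding. The CI half-width is (12.107 − 2.357)/2 = 4.875. With 28 degrees of freedom (t = 2.048), SE = 4.875/2.048 = 2.38 and t = 7.23/2.38 = 3.04, giving p = 0.005, which rounds to the printed 0.01.

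**2. Baseline CARS.** Pooled SD = √[(15 × 5.7² + 13 × 7.2²)/28] = 6.44. The gap is 43.5 − 40.6 = 2.9 points, or 2.9/6.44 = 0.45 SD. With √(1/16 + 1/14) = 0.366, SE = 6.44 × 0.366 = 2.36, t = 1.23 and p = 0.23. The SAP's statement is correct as a test result, yet the observed gap is nearly half a standard deviation.

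**3. What non-significant covers at 16 v 14.** A standardised difference reaches significance only above 2.048 × 0.366 = 0.75 SD. For CARS that is 0.75 × 6.44 = 4.8 points, so a baseline gap larger than the SAP's own 4.5-point responder threshold could still be reported as not significant. For a yes/no variable, an observed split of 12/16 v 5/14 (75% v 36%) gives Fisher p = 0.063, also not significant.

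**4. Possible effect on the result.** The SD of change implied by the printed interval is 2.38/0.366 = 6.50. An observed imbalance of 0.5 SD in a covariate with correlation r to change shifts the difference by 0.5 × r × 6.50:
- r = 0.3: 0.98 points
- r = 0.5: 1.63 points

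This is about 13% to 22% of 7.23. If the shift is in the unfavourable direction and the interval width is unchanged, the lower limit moves from 2.357 to 1.38 or 0.73. Reaching zero would need r = 2.357/(0.5 × 6.50) = 0.725.

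The therapy-adjusted estimate itself cannot be computed, because no therapy data are given.

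**The case against.** **The commitment may not govern this trial.** It stands in the protocol of a one-arm follow-up, which has no control condition, while the SAP reports a two-arm comparison. This stands. A reader might infer that the SAP broke a binding commitment, but the documents do not establish that. However, a sentence about control and experimental conditions can apply only to a comparison of the kind the SAP reports, so the sponsor must say which study it governs.

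**The SAP does not claim what a reader might infer.** It is tempting to read it as declaring the groups comparable because the tests were non-significant, or as using those tests in place of adjustment. It says neither; it reports the tests and then an unadjusted analysis. The point does not depend on motive.

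**Power figures would overstate the case.** At 16 v 14, a t-test has 26% power for a 0.5-SD difference, so a reader might say that such an imbalance is missed 74% of the time. That describes a difference between hypothetical populations, and only for a continuous variable; gender and ethnicity are categorical. The estimate is biased by the imbalance actually observed in these 30 children. For the same reason, the 95% CI for the baseline CARS gap (−1.9 to 7.7) does not mean that the sample may hide a 7-point imbalance. The sample gap is 2.9.

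**Matching would help.** If section 14.0's matching on age, gender and therapy hours was applied in the reported trial, large imbalances in them are less likely. That stands, but variables used in assignment normally belong in the analysis, so it also supports the proposed model.

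**Table 1 is not visible.** It may already give baseline figures by group, so their absence cannot be asserted.

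**The demonstrated gap is in CARS, not therapy.** Correct. It is used here only to show what a non-significant result can cover; whether baseline CARS should be a covariate is a separate question.

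**Conclusion.** The point holds in this form: the protocol text announces control for behavioural therapy, the visible SAP has none, and the non-significant baseline tests do not show that it was unnecessary. The 0.75-SD cut-off and the 0.45-SD CARS gap follow from the SAP's figures, assuming two-sided 5% tests.

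The effect on the result is an assumption, not a finding. A shift of 1.0 to 1.6 points needs an observed 0.5-SD imbalance and a correlation of 0.3 to 0.5 with change, and its direction is unknown. A reader might infer that the efficacy result is explained by unbalanced therapy. The documents do not support that: they show no therapy imbalance, and under these assumptions the lower limit stays above zero. This is a change the sponsor should make, not a reason to set the result aside.

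**What to change.** 1. State which study inclusion criterion 3 and the matching sentence in section 14.0 govern, and reconcile them with the one-arm design in sections 1.0, 7.2 and 7.6.
2. For the two-arm comparison, report beside the unadjusted 7.23 the Active-minus-Sham difference in CARS change, with 95% CI, from a linear model containing therapy and age. Use therapy hours if they were recorded in that trial, otherwise treatment status, with its definition given. Include both covariates whatever their baseline p-values, and rest the conclusion on both estimates.
3. Do not use baseline significance tests as evidence of comparability. Where Table 1 does not already do so, give group summaries and observed standardised differences for each baseline variable (for CARS: 2.9 points, 0.45 SD).

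**Cost.** Some rewording and one extra regression. The SAP's baseline statement indicates that age and treatment status were recorded in the reported trial; the documents do not establish this for therapy hours. The model uses about two of the 28 degrees of freedom, and the adjusted estimate may be less favourable than 7.23.

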### Primary Outcome

Every participant who completed the trial was evaluated with CARS post-treatment. There were no missing CARS posttreatment evaluations. In the Active group, the before treatment CARS scores had a mean score value of 43.5 (n = 16) with a standard deviation (SD) of 5.7, the after-treatment scores had a mean score of 33.7 with an SD of 5.0. In the Sham group, the before treatment CARS scores had a mean score value of 40.6 (n = 14) with SD of 7.2, the after-treatment scores had a mean score of 38.0 with SD of 8.4. Table 3 shows the mean (M) and SD of the CARS scores for the Active and Sham groups before and after treatment. The difference in the change in CARS between the two groups was 7.23 (95% CI 2.357 to 12.107, p=0.01).

In addition to analyzing the changes in CARS scores based on averages, we also conducted respondents-based analyses, quantifying the number of participants in Active and Sham groups, whose change in CARS was greater than 4.5 points (as it has been suggested by Jurek et al 2022 to be the minimal clinically important difference). The result was significant  $\chi^2=8.48$ ,  $p=.004$ . By the end of the trial, 87% of the participants in the Active group (14) had achieved an equal or greater than 4.5-point reduction in CARS scores, only 35% of the participants of Sham group (5) achieved an equal or greater than 4.5-point reduction in CARS scores. The number of subjects that achieved this minimal clinically important difference in the Active group was statistically significantly higher compared to the Sham group. Therefore, the treatment was considered to have clinically meaningful efficacy.

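### The SAP's responder result uses two different 4.5-point rules, and its chi-square of 8.48 does not follow from its own counts (minor; the printed counts stay significant)

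*SAP*

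**What the plan says.** The responder analysis appears in the SAP under Primary Outcome, after the comparison of mean CARS change. The sentence that introduces it counts children "whose change in CARS was greater than 4.5 points" and ties the threshold to a published minimal clinically important difference. The next sentence reports "The result was significant", with chi-square 8.48 and p=.004. The counts follow: "87% of the participants in the Active group (14) had achieved an equal or greater than 4.5-point reduction in CARS scores", and "only 35% of the participants of Sham group (5" participants) met the same rule, again worded as "achieved an equal or greater than 4.5-point reduction in CARS scores". The paragraph ends: "Therefore, the treatment was considered to have clinically meaningful efficacy".

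The SAP's Primary Analyses section names only an independent-sample t-test on CARS change. It sets out no responder rule and no test for one, so the wording under Primary Outcome is the only definition available. That wording does not name the chi-square variant, say which inequality produced 8.48, or give the number of children who changed by exactly 4.5 points.

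**The concern.** There are two defects in one short paragraph.

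- **Definition.** The rule is strict where the test is introduced and inclusive where the counts are given. The sentence on the test also speaks of a change and the sentence on the counts of a reduction; only the latter gives a direction. A child who improved by exactly 4.5 points is a responder under one sentence and not under the other.
- **Statistic.** The printed chi-square and p-value agree with each other but not with the counts printed beside them.

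The SAP draws its statement of clinical meaning directly from this comparison. As it stands, a reader cannot tell who counts as a responder, nor reproduce the statistic offered as evidence.

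**Working it through.** **Inputs (SAP, Primary Outcome).** Active n = 16 with 14 responders; Sham n = 14 with 5 responders. No post-treatment CARS score is missing, so the denominators are 16 and 14. Printed result: chi-square 8.48, p=.004. A two-sided 5% level is assumed, because the SAP states none for this test.

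**Percentages.** 14/16 = 87.5%, printed as 87%; 5/14 = 35.7%, printed as 35%. Both are truncated, not rounded.

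**The printed pair.** A chi-square of 8.48 on 1 degree of freedom has p = .0036, which rounds to .004. The statistic and p-value are consistent with each other.

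**From the counts.** The table is Active 14 yes, 2 no; Sham 5 yes, 9 no. The column totals are 19 and 11, and N = 30.

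- Cross-product difference: 14×9 − 2×5 = 116.
- Denominator: 16×14×19×11 = 46,816.
- Pearson: 30×116² / 46,816 = 403,680 / 46,816 = 8.62, p = .0033.
- Yates: 30×(116 − 15)² / 46,816 = 306,030 / 46,816 = 6.54, p = .011.

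| Test on 14/16 vs 5/14 | Statistic | p |
|---|---|---|
| Pearson | 8.62 | .0033 |
| Yates | 6.54 | .011 |
| Likelihood ratio | 9.12 | .0025 |
| Chi-square with N − 1 | 8.34 | .0039 |
| Wald on log odds ratio | 7.27 | .007 |
| Fisher exact, two-sided | – | .0068 |
| Printed in the SAP | 8.48 | .004 |

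Pearson computed from the printed 87% and 35% gives 8.64. None of these is 8.48. The gap from Pearson is 8.62 − 8.48 = 0.14, about 1.7%.

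**Could another table give 8.48?** All tables with 16 and 14 children were searched under Pearson, Yates and likelihood ratio. None rounds to 8.48. With Active ahead, the nearest are:

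- 14/16 vs 4/14, Yates: 30×(14×10 − 2×4 − 15)² / (16×14×18×12) = 30×117² / 48,384 = 8.4877, p = .0036;
- 13/16 vs 3/14, Yates: 8.467, p = .0036.

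The first would print as 8.48 if truncated, as the percentages were. It is the table that a strict rule would give if one Sham child and no Active child improved by exactly 4.5 points.

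**What ties at exactly 4.5 would do.** Assume that 14 and 5 are the inclusive counts and that the scoring allows a change of exactly 4.5, which the documents do not say. The strict rule then removes the ties:

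| Ties (Active, Sham) | Strict counts | Pearson p | Yates p | Fisher p |
|---|---|---|---|---|
| 0, 0 | 14/16 vs 5/14 | .003 | .011 | .007 |
| 0, 1 | 14/16 vs 4/14 | .001 | .004 | .002 |
| 1, 0 | 13/16 vs 5/14 | .011 | .030 | .024 |
| 1, 1 | 13/16 vs 4/14 | .004 | .011 | .009 |
| 2, 0 | 12/16 vs 5/14 | .030 | .072 | .063 |
| 2, 1 | 12/16 vs 4/14 | .011 | .030 | .026 |
| 3, 0 | 11/16 vs 5/14 | .070 | .149 | .141 |

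**Effect size on the printed counts.** Risk difference 87.5% − 35.7% = 51.8 percentage points. Newcombe's interval, built from the Wilson limits (64.0% to 96.5% Active, 16.3% to 61.2% Sham), is about 17 to 73 points.

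**The case against.** The strongest reply is that nothing of substance turns on this. The printed counts are significant on every test tried, and 8.48 differs from Pearson by under 2%. The chi-square directly follows the strict wording, so the natural reading is that it is the strict-rule result, with the inclusive counts printed after it. On that reading both rules give p below .05, and the nearest table, 14/16 versus 4/14, is a stronger result than the printed counts. The responder comparison is also an addition to the mean-change comparison (7.23 points, 95% CI 2.357 to 12.107), which this point does not touch.

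Most of this stands, and it limits the point to a reporting correction. It does not remove it: if the reply is right, the test and the counts do use different definitions, and the SAP does not say so. The truncation explanation fits but cannot be proved from the documents.

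Two stronger readings are tempting, and the documents support neither.

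- **That a few ties could cost the result its significance.** This needs at least two Active children (Fisher or Yates) or three (Pearson) at exactly 4.5 and no Sham child there. None of those tables gives a statistic near 8.48, Sham ties push the other way, and no number of ties is reported.
- **That the ambiguous rule carries into the present study.** The protocol describes a one-arm, open-label study (sections 1.0 and 7.2). Its planned quantitative analysis is repeated-measures t-tests on total CARS2 (section 7.6). No responder analysis is planned in the text available.

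A preference for Fisher over Pearson is optional here: the smallest expected count is 14×11/30 = 5.13.

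**Conclusion.** The point holds as a minor error. The SAP states two responder rules, and its chi-square of 8.48 (p=.004) is not what its counts give: Pearson is 8.62 (p=.003), Yates 6.54 (p=.011) and Fisher p=.007. The test and the counts may rest on different cut-offs; only the individual scores can settle that.

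The direction of the conclusion is not shown to change. At the printed counts every standard test is below .05, on the assumed two-sided 5% level. The effect of the cut-off depends on how many children in each arm changed by exactly 4.5 points. That number is not given, and it could move the result either way.

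**What to change.** In the SAP, under Primary Outcome:

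1. State one responder definition, as a reduction in CARS with one inequality, and use it both where the test is introduced and where the counts are given.
2. Recompute the counts and the test from the individual scores under that definition.
3. Name the test and replace 8.48 and .004 with the matching result. If 14/16 and 5/14 are confirmed, that is Pearson 8.62, p=.003, or Fisher exact p=.007.
4. Add the risk difference and its interval: for those counts 52 percentage points, Newcombe 95% CI about 17 to 73.
5. Give the counts under the other inequality in one sensitivity line, which also shows how many children sat at exactly 4.5.

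The cost is a change of wording and a short recalculation, with no new data. The reported p-value may move slightly in either direction, depending on the test named and the definition chosen.
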